6.3 Secondary Efficacy Endpoints for Non-Flare-up Based Treatment

Efficacy data for non-flare-up based treatment assessments will generally be presented in total for the WBCT Population.

Secondary efficacy endpoints for non-flare-up based treatment include:

1. Change from baseline in whole body burden of HO as assessed by low-dose WBCT scan, excluding head, at Study Months 12 and 24.
2. Change from baseline in ROM as assessed by CAJIS at Study Months 12 and 24.
3. Change from baseline in physical function using age-appropriate forms of the FOP-PFQ at Study Months 12 and 24.
4. Change from baseline in physical and mental health using age-appropriate forms of the PROMIS Global Health Scale at Study Months 12 and 24.
5. Change from baseline in the use of assistive devices and adaptations for daily living by FOP subjects at Study Months 12 and 24.
6. Change from baseline in biomarkers at Study Months 12 and 24.

Baseline is Part B Screening.

6.3.1 Whole Body Burden of HO

Whole body burden (volume) of HO will be determined from the WBCT scan. HO will be assessed at 15 locations including head and neck, left and right elbow, left and right hip, left and right knee, left and right shoulder, left and right distal lower extremities, left and right distal upper extremities, lower spine/abdomen, and upper spine/chest.

Whole body burden of HO will be calculated as the sum of the volumes for each location. If there is no HO, 0 will be assigned for analysis.

Volume of HO and change from baseline (total and by region) will be summarized for subjects with any new HO at Month 12 and no new HO at Month 12, with descriptive statistics by the following subsets: Treated Flare-ups, Under/Untreated Flare-ups, and No Flare-ups.

6.3.2 Volume of HO

The change from baseline in the amount of new HO formed at the original flare-up site will be summarized and provided in a listing.

7 Safety Data

Adverse events will generally be presented by treatment group (PVO 20/10 mg only (including weight-adjusted doses); PVO 20/10 mg (including weight-adjusted doses) with prior non-flare-up treatment; and non-flare-up treatment only) and in total for the Enrolled and Treated Populations. The treatment groups will be based on when the AE occurred and will correspond to the following groups: No treatment (prior to any treatment or between flares if not on non-flare-up dosing), Non-flare-up treatment, and Flare-up treatment PVO 20/10 mg (including weight-adjusted doses).

Safety data for flare-up based treatment assessments will generally be presented by cohort and in total for the Flare-up Population. Baseline is Flare-up Day 1 (the date of first dose of flare-up treatment).

Safety data for non-flare-up based treatment assessments will generally be presented in total for the Non-Flare-up Treated Population (the date of first dose of non-flare-up treatment; Non-flare-up Day 1). Baseline is Part B Screening/Baseline.

7.1 Adverse Events

Adverse events will be recorded from the time informed consent (Part B Study Day 1) is signed through study completion. All AEs will be coded to body system and preferred term using MedDRA Version 17.0. At least possibly related AEs are defined as AEs assessed by the Investigator as possibly, probably, or definitely related to study drug. Adverse events that require Common Terminology Criteria for Adverse Events (CTCAE) grading (Version 4.03, 14 June 2010) as indicated on the eCRF are considered to be retinoid-associated AEs.

Adverse events with start date on or after Flare-up Day 1 and on or before the date of completion for the Flare-up treatment will be attributed to the Flare-up Treatment Period. Adverse events with start date on or after Non-Flare-up Day 1 for which the patient is not undergoing flare-up treatment will be attributed to the Non-Flare Treatment Period. Adverse events with start date on or after Study Day 1 that are not attributed to the flare-up or non-flare-up treatments will be attributed to the Non-Treatment Period.

For the both the Enrolled Population and the Treated Population, AEs will be summarized by period (Non-Treatment Period, Non-Flare Treatment Period, Flare-up Treatment Period) and in total.

The incidence of the following AEs will be summarized with counts and percentages of subjects (overall and by MedDRA body system and preferred term):

- Any AEs
- Any AEs by maximum severity
- Any AEs at least possibly related to study drug
- Any AEs at least possibly related to study drug by maximum severity
- Any retinoid-associated AEs
- Any retinoid-associated AEs at least possibly related to study drug
- Any retinoid-associated AEs by maximum CTCAE grading
- Any retinoid-associated AEs by maximum severity
- Any retinoid-associated AEs by seriousness
- Any serious adverse events (SAEs)
- Any severe/life threatening retinoid-associated AE by maximum CTCAE grading
- Any AEs leading to dose modification or interruption of study drug
- Any AEs leading to discontinuation of study drug
- Any AEs leading to discontinuation of study

Data listings will be provided for (1) all AEs, (2) SAEs, (3) AEs leading to dose modification or interruption of study drug, (4) AEs leading to discontinuation of study drug, and (5) AEs leading to discontinuation of study. Part B Study Day and/or Flare-up Day for AE start and stop dates will be included on AE listings as appropriate.

7.1.1 Number of Flare-ups Per Subject-Month

Flare-ups are counted using the number of subject/Investigator-reported flare-ups and AEs with the ‘condition aggravated’ preferred term that are medically reviewed and classified as unique flare-ups (not treated with palovarotene and not recorded as a subject/Investigator-reported flare-up). Rates will be calculated by dividing the total number of flare-ups by the total subject months of follow-up.

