2.1.2 Secondary Objectives

- To evaluate the effect of palovarotene to prevent HO as assessed by low-dose, whole body computed tomography (WBCT) scan, excluding head.
- To evaluate the effect of palovarotene on active range of motion (ROM) at the flare-up site as assessed by goniometer.
- To evaluate the effect of palovarotene on ROM as assessed by the Cumulative Analogue Joint Involvement Scale (CAJIS) for FOP.
- To evaluate the effect of palovarotene by the subject and Investigator global assessment of movement at the flare-up site.
- To evaluate the effect of palovarotene on physical function using age-appropriate forms of the FOP Physical Function Questionnaire (PFQ).
- To evaluate the effect of palovarotene on physical and mental health using age-appropriate forms of the Patient Reported Outcomes Measurement Information System (PROMIS) Global Health Scale.
- To evaluate the effect of palovarotene on pain and swelling associated with the flare-up using numeric rating scales (NRS) or the Facial Pain Scale-Revised (FPS-R) in subjects under 8 years of age.
- To evaluate the effect of palovarotene on the use of assistive devices and adaptations for daily living by FOP subjects.
- To evaluate the effects of palovarotene on soft tissue swelling and cartilage formation at the flare-up site as assessed by magnetic resonance imaging (MRI); or the effect of

palovarotene on soft tissue swelling as assessed by ultrasound (US) in subjects unable to undergo MRI.

- To evaluate bone, cartilage, angiogenesis, and inflammation biomarkers and explore correlations between changes from baseline in biomarkers and clinical efficacy.
- To evaluate the pharmacokinetics of palovarotene during the first treated flare-up.
- To evaluate the ability of different dosing regimens of palovarotene to prevent new flare-ups.
- To evaluate the long-term safety and efficacy of prior palovarotene treatment at the original flare-up site in Study PVO-1A-201; efficacy will be based on the amount of new HO formed at the original flare-up site as assessed by low-dose CT scan (or plain radiographs in subjects unable to undergo CT scan) in the Pediatric Cohort or low-dose whole body CT scan, excluding head, in the Adult Cohort.

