2.2 Study Population

A total of approximately 60 subjects will be enrolled in Part B including approximately 40 subjects who completed Study PVO-1A-201 and up to 20 new Adult Cohort subjects. The Adult Cohort will include subjects with at least 90% skeletal maturity, regardless of age; the Pediatric Cohort will include subjects with less than 90% skeletal maturity, regardless of age. Any Pediatric Cohort subject who achieves $\geq 90\%$ skeletal maturity during Part B may be considered for enrollment into the Adult Cohort at the discretion of the Investigator.

Flare based analyses will include the treatment groups: PVO 20/10 mg, Prior Non-Flare-up/PVO 20/10 mg, and Combined PVO 20/10 mg (=PVO 20/10 mg + Prior Non-Flare-up/PVO 20/10 mg groups). PVO 20/10 mg is defined as flare-ups that did not have prior non-flare-up treatment. Prior Non-Flare-up/PVO 20/10 mg is defined as flare-ups that were treated with Non-Flare-up 5 mg treatment prior to the start of the flare-up treatment. It is important to mention that the flare-up analyses is based on flare-ups, thus subjects may be included in both treatment groups, depending on when non-flare-up dosing began.

WBCT analyses are based on the PVO Non-Flare-up/PVO 20/10 mg treatment group and will include the following subsets: Treated Flare-ups, Under/Untreated Flare-ups, No Flare-ups, and Combined Treated/No Flare-ups.

Only subjects with Non-Flare-up treatment are imaged using WBCT, thus only the PVO Non-Flare-Up/PVO 20/10 mg treatment group is present. This treatment group is subset into 3 different treatment groups, depending on whether or not the subjects had treated, untreated or no flares during the duration between the baseline and Month 12 WBCT scans. Treated Flare-ups are defined as subjects who received non-flare-up/flare-up regimen for all flare-ups. Under/Untreated Flare-ups are defined as subjects who did not receive palovarotene dosing for all flare-ups. No flare-ups are defined as subjects who received the non-flare-up regimen and did not report any flare-ups.

Safety treatment groups include the PVO 20/10 mg and Non-Flare-up 5 mg groups.

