2.4 Study Treatment

Subjects in the Adult Cohort were scheduled to be treated with 5 mg palovarotene daily for up to 24 months (non-flare-up based treatment); however, some adult subjects chose not to receive non-flare-up based treatment.

Flare-up based treatment will begin as soon as possible after a subject reports onset of a flare-up and the flare-up has been confirmed by the Investigator. In the event of an eligible flare-up, subjects in the Adult Cohort will receive open-label palovarotene treatment as follows:

- 20 mg for 28 days. The first dose will be taken upon flare-up confirmation by the Investigator.
- 10 mg for 56 days, for a total flare-up treatment duration of 84 days; treatment may be extended if the flare-up is ongoing and continue until the flare-up resolves. Dosing will be extended in 4-week intervals and be based on clinical signs and symptoms as assessed by the Investigator.

Subjects not receiving non-flare-up based dosing will only be treated during eligible flare-ups and will receive weight-adjusted doses of 20 and 10 mg palovarotene as follows:

Weight Range Category	20-mg Equivalent	15-mg Equivalent	10-mg Equivalent	7.5-mg Equivalent*	5-mg Equivalent*
20 to <40 kg	12.5 mg	10 mg	6 mg	4 mg	3 mg
40 to <60 kg	15 mg	12.5 mg	7.5 mg	5 mg	4 mg
≥60 kg	20 mg	15 mg	10 mg	7.5 mg	5 mg

* In the event of dose de-escalation.

If the subject experiences intolerable side effects during flare-up based dosing, the dose may be reduced to the next lower dose; if the subject is already receiving the lowest possible dose, then study drug will be discontinued. Treatment may be extended after the 84-day treatment period (flare-up based dosing) if the flare-up is ongoing and continue until the flare-up resolves. Dosing will be extended in 4-week intervals based on clinical signs and symptoms as assessed by the Investigator, with remote visits performed every 2 weeks while on treatment. In the event the subject requires dose de-escalation due to an intolerable side effect for a previous flare-up, then the dose the subject will receive for a subsequent flare-up will be determined by the Investigator and the Medical Monitor.

After the Flare-up Day 84/EOT visit has been conducted and the flare-up is considered resolved, subjects in the Adult Cohort will resume the non-flare-up based treatment.

Subjects not receiving non-flare-up based dosing who do not experience an eligible flare-up will not be treated.

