$AUC_{0-24(ss)}$	Area under the concentration versus time curve over the 24-hour dosing interval; calculated using linear trapezoid rule.
$C_{max(ss)}$	Maximum or peak measured plasma concentration at steady-state.
$C_{min(ss)}$	Minimum or trough measured plasma concentration at steady-state.
$T_{max(ss)}$	Time of maximum or peak measured plasma concentration at steady-state, obtained by inspection.
CL/F	Clearance defined as: $Dose/AUC_{0-24(ss)}$.
λ_z	Terminal rate constant
$t_{1/2z}$	Apparent terminal elimination half-life; calculated as $\ln(2)/\lambda_z$. The number of data points included in the regression will be determined by visual inspection, but a minimum of three data points in the terminal phase, excluding C_{max} , will be required to estimate λ_z .

9 Changes from Protocol

For the purposes of clarity and consistency of nomenclature, the Flare-up Rate Population described in the protocol was renamed as the Non-Flare Treated Population.

The initial secondary objective listed in Section 2.1.2 was not included in Amendment 3 of the protocol for Study PVO-1A-202 Part B or Amendment 1 of the protocol for Study PVO-1A-204.

The protocol describes the primary comparison of outcomes to be from data collected from the NHS and Phase 2 study. These comparisons will be performed in a future analysis and the analysis described here will instead focus on comparisons solely from Study PVO-1A-202 Part B between treatment groups of PVO 20/10 mg and Prior Non-Flare-up/PVO 20/10 mg, for flare based analyses; and treatment groups of treated, untreated, or no-flares, for WBCT based analyses.

10 References

3. D'Agostino, RB., Jr., Tutorial in Biostatistics: Propensity Score Methods for Bias Reduction in the Comparison of a Treatment to a Non-Randomized Control Group. *Statistics in Medicine*, 1998, 17, 2265-2281.

Appendices

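### Part B's only flare-up rate is not split by dosing regimen, so as written it cannot show whether any regimen prevents new flare-ups

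*SAP*

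**What the plan says.** All references are to the Part B SAP unless Part C is named.

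- **Objective (2.1.2).** One secondary objective is "To evaluate the ability of different dosing regimens of palovarotene to prevent new flare-ups". It concerns regimens in the plural, so it calls for a contrast.
- **Rate (7.1.1).** The count takes flare-ups reported by the subject or investigator and adds events coded to the condition-aggravated preferred term that medical review has "classified as unique flare-ups (not treated with palovarotene and not recorded as a subject/Investigator-reported flare-up"). Then: "Rates will be calculated by dividing the total number of flare-ups by the total subject months of follow-up". The section names no population, period, cohort, comparator or interval.
- **Adverse event periods (7.1).** "AEs will be summarized by period (Non-Treatment Period, Non-Flare Treatment Period, Flare-up Treatment Period) and in total". The measure is stated next: "The incidence of the following AEs will be summarized with counts and percentages of subjects".
- **Flare-based groups (2.2).** These are defined on flare-ups: "PVO 20/10 mg is defined as flare-ups that did not have prior non-flare-up treatment". One subject can contribute to both groups.
- **Treatment (2.4).** Daily 5 mg was scheduled for the Adult Cohort, but "some adult subjects chose not to receive non-flare-up based treatment". Subjects not on 5 mg are treated only during eligible flare-ups.
- **Changes from protocol (Section 9).** For consistency of naming, "the Flare-up Rate Population described in the protocol was renamed as the Non-Flare Treated Population". Section 7.1.1 does not mention that population under either name.

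**The concern.** Part B follow-up is mixed by design. Some time is off drug, some is on daily 5 mg and some is on 20/10 mg for a flare-up, and a subject can pass through all three. A ratio of total events to total months averages over them.

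If daily 5 mg lowered the flare-up rate, the average would not show it. If 5 mg raised the rate, the average would not show that either. The single figure could also be quoted as the flare-up rate on palovarotene, although part of its denominator may be time without drug. A stated secondary objective would then have no analysis able to address it.

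**Working it through.** The plan states no flare-up rate, sample size or power for this analysis, so there is no figure of its own to reproduce. The check has four steps.

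**1. Does any other Part B analysis fill the gap?**

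- The endpoint lists in 6.2 and 6.3 contain no flare-up frequency endpoint.
- Section 5.6 counts treated flare-ups in subjects who had at least one, which cannot measure prevention. Untreated flare-ups are only listed.
- Sections 7 and 7.1 divide adverse events by what the subject was receiving, but report percentages of subjects. No subject-time per period is defined as a denominator.
- The groups in 2.2 are sets of flare-ups and carry no subject-time.

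That leaves 7.1.1.

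**2. What can the pooled rate identify?** Let s be the share of subject-time and r the rate in each state:

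pooled rate = s(off) × r(off) + s(5 mg) × r(5 mg) + s(20/10) × r(20/10)

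This is one equation in three unknown rates. With assumed shares of 0.30, 0.50 and 0.20 and a pooled rate of 0.10 per month:

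| Scenario | Off drug | 5 mg | 20/10 mg | Pooled |
|---|---|---|---|---|
| No effect | 0.100 | 0.100 | 0.100 | 0.10 |
| Both regimens halve the rate | 0.154 | 0.077 | 0.077 | 0.10 |
| 5 mg doubles it, 20/10 mg has no effect | 0.067 | 0.133 | 0.067 | 0.10 |
| 5 mg halves it, 20/10 mg doubles it | 0.105 | 0.053 | 0.211 | 0.10 |

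Check of the second row: 0.30 × 0.154 + 0.50 × 0.077 + 0.20 × 0.077 = 0.046 + 0.039 + 0.015 = 0.10. The same ambiguity appears with shares of 50/30/20 and 20/50/30, and with pooled rates of 0.05 and 0.20.

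**3. How mixed might one subject's time be?** Take an adult followed for 24 months with one 84-day flare-up treatment (84/30.5 = 2.75 months).

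- If 5 mg starts on Day 1, as in the compliance example in 5.9: (24 − 2.75)/24 = 89% of time on 5 mg.
- If 5 mg starts at month 6, an assumption: (24 − 6 − 2.75)/24 = 64%.

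The share therefore runs from about 64% to 89% across these two starts, and is zero for an adult who declined 5 mg.

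**4. Would a split rate be informative?** Section 2.2 plans about 60 subjects and Section 2.3 about 18 to 24 months each, giving 60 × 18 = 1,080 to 60 × 24 = 1,440 subject-months. Use the 30/50/20 shares, equal rates in each state and Poisson counts, with SE(log rate ratio) = √(1/e1 + 1/e2), where e1 and e2 are the event counts off drug and on 5 mg. The 95% interval for 5 mg versus off drug is the estimate multiplied and divided by:

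| Assumed rate per month | 1,080 months | 1,440 months |
|---|---|---|
| 0.05 | 1.85 | 1.70 |
| 0.10 | 1.55 | 1.46 |
| 0.20 | 1.36 | 1.31 |

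For the first cell: e1 = 1,080 × 0.30 × 0.05 = 16.2 and e2 = 1,080 × 0.50 × 0.05 = 27. SE = √(1/16.2 + 1/27) = 0.314, and exp(1.96 × 0.314) = 1.85. Repeated flare-ups within a subject would usually widen these intervals.

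**The case against.** The best reply is that 7.1.1 never says there will be one overall rate. It speaks of rates in the plural and sits under 7.1, where three treatment periods are defined. Part of its count consists of adverse events, to which those periods already apply, so a programmer could reasonably produce rates by period. This stands to a degree: the pooling follows from the two totals and the absence of any split, and is not stated outright. But 7.1.1 does not invoke the periods, the period rule serves percentages of subjects, and reported flare-ups are counted separately from adverse events. Part C, in its Section 5.8, does say how its flare-up rate is to be divided.

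A second reply is that Part B is descriptive, with no modelling, and that Section 9 defers the protocol's primary external comparisons. That is so, but a descriptive rate by period needs no model, and Section 9 does not drop this objective.

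A third reply is that splitting will not give a clean answer. This stands in full. The comparison is non-randomised. Because 5 mg is scheduled only for adults, time without drug comes largely from the Pediatric Cohort, adults who declined 5 mg and time before the first dose. Time on 20/10 mg begins because a flare-up occurred.

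Two stronger readings are tempting, and the document supports neither. A reader might infer that follow-up starts at consent, so that months before the first 5 mg dose must be in the denominator. Section 7.1.1 does not define the start, and Section 3.7 defines both a consent-based day and a day counted from the first 5 mg dose. A reader might also infer from Section 9 that the protocol's rate population was detached from this rate. Section 9 reports only a renaming, and the protocol is not at hand to show what the link was.

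**Conclusion.** The point holds for the text as written: Part B states an objective about regimens, and its only flare-up rate names no population and has no regimen split. Taken literally, that rate cannot distinguish benefit, no effect and harm.

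The non-identifiability does not depend on the assumed numbers; one weighted average cannot return its components. The illustrative rates, the time shares and the 64% to 89% range for time on 5 mg are assumptions, and the plan gives no values against which to test them.

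It would go too far to say that the trial's data cannot address the objective, or that a split would reveal the true effect of 5 mg. The dosing and flare-up dates already used elsewhere in the plan allow a split. Under the assumptions above, the 5 mg versus no-drug ratio would be known to within a factor of roughly 1.3 to 1.85 before allowing for within-subject correlation. That is informative but imprecise, and open to selection.

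**What to change.** In 7.1.1:

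1. Name the population and define when follow-up starts and ends.
2. Assign each flare-up by its onset date, and each subject-day, to exactly one of the three periods in 7.1: Non-Treatment, Non-Flare Treatment or Flare-up Treatment. Use onset and not first treatment day, so that a flare-up is not credited to the treatment it triggered. State where days after 5 mg has stopped belong.
3. Report events, subject-months and rate for each period, overall and by cohort, with a 95% confidence interval that allows for repeated flare-ups in a subject, for example a subject-level bootstrap.
4. Keep the pooled rate as a descriptive total.
5. Label the 5 mg versus no-drug comparison exploratory, giving the reasons: no randomisation, 5 mg scheduled only for adults, and some adults declining it. State that the rate during 20/10 mg time is not a measure of prevention, because that time begins with a flare-up.

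The cost is a short change of wording and a little programming from dates already collected. The downside is wide intervals, most of all within cohort.

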7.2 Safety Laboratory Assessments

Values and changes from baseline will be summarized at each scheduled visit with descriptive statistics. Both the change from Screening/Baseline (patient based) and the change from Flare-up Day 1 (flare-up based) will be presented. Mean values (+/- standard error) will be plotted over time for all laboratory parameters and biomarkers. If multiple records occur within a post-baseline visit, the first non-missing value will be used. Note that results obtained locally rather than from the central laboratory will not be used to calculate change from baseline and will be excluded from these summaries.

Potentially clinically significant values at baseline and new-onset potentially clinically significant (PCS) values post-baseline will be summarized with counts and percentages of subjects or flare-ups as appropriate. Separate analyses will be performed for the non-flare-up treatment visits and the flare-up treatment visits. New-onset PCS values are defined as values that were not PCS at baseline and were PCS post-baseline. Note that results obtained locally will be included in these summaries. PCS values are defined in Table 4.

Table 4. Potentially Clinically Significant Safety Laboratory Values

	PCS Low	PCS High
Biochemistry		
Aspartate aminotransferase	N/A	3 x ULN
Alanine aminotransferase	N/A	3 x ULN
Amylase	N/A	3 x ULN
Lipase, pancreatic	N/A	3 x ULN
Bilirubin	N/A	>2 mg/dL
Thyroxine	<4.0 mcg/dL	>13.0 mcg/dL
Lipids		
Cholesterol	N/A	>300 mg/dL
Triglycerides	N/A	>400 mg/dL
Hematology		
Leukocytes	<2.8 x 10 ⁹ /L	>16.0 x 10 ⁹ /L
Hemoglobin (females)	<9.5 g/dL	>17.5 g/dL
Hemoglobin (males)	<11.5 g/dL	>19.0 g/dL
Hematocrit (females)	<32%	>54%
Hematocrit (males)	<37%	>60%
Platelets	<75 x 10 ⁹ /L	>700 x 10 ⁹ /L

A listing will be provided for all subjects with PCS lipase values that will include all lipase results during the study along with associated palovarotene and glucocorticoid dosing data (dose and start and stop dates). A by-subject listing of all laboratory parameters will be generated.

